5.1 Definition for Analysis Populations

RZB Population:

The RZB population consists of subjects who were randomized to risankizumab 150 mg in Studies 1311.3, 1311.30, 1311.28, 1311.38, and M16-178. This population will be used to evaluate the long-term safety and efficacy of risankizumab 150 mg with loading dose. For subjects from Japan, data after the first dose of risankizumab 150 mg from the preceding studies, and prior to the start of 75 mg dose will be used for the analyses.

RZB_NL Population:

The RZB_NL population consists of subjects who were randomized to placebo in the initial study and switched to risankizumab 150 mg (without loading dose) in Studies 1311.3, 1311.4, 1311.28, and 1311.38. This population will be used to evaluate the long-term safety and efficacy of risankizumab 150 mg without initial loading dose. For subjects from Japan, data after the first dose of risankizumab 150 mg from the preceding studies, and prior to the start of 75 mg dose will be used for the analyses.

Retreatment Population:

The Retreatment population consists of subjects who were re-randomized to placebo in Part B of Study 1311.4 and received retreatment of risankizumab 150 mg. This population will be used to evaluate the safety and efficacy of re-treatment after temporary withdrawal. For subjects from Japan, data after the re-treatment and prior to the start of 75 mg dose will be used for the analyses.

UST_RZB Population:

The UST_RZB population consists of subjects who were randomized to ustekinumab in Studies 1311.3 and 1311.28. This population will be used to assess the safety and efficacy of risankizumab 150 mg when subjects switch from ustekinumab to risankizumab

150 mg. For subjects from Japan, data prior to the start of 75 mg dose will be used for the analyses.

ADA RZB Population:

The ADA_RZB population consists of subjects who were randomized to adalimumab in Study 1311.30 and switched to risankizumab. This population will be used to assess the safety and efficacy of risankizumab when subjects from adalimumab to risankizumab.

FUM RZB Population:

The FUM_RZB Population consists of subjects who were randomized to Fumaderm[®] (fumaric acid esters) in Study M16-178. This population will be used to assess the safety and efficacy of risankizumab when subjects switch from Fumaderm[®] to risankizumab.

RZB Japan Population:

The RZB Japan Population consists of subjects from Japan during the visits in the OLE period, regardless of dose. This population will be used to assess safety and efficacy during the OLE period, regardless of dose. The RZB Japan Population will only be analyzed in the final analysis, upon study completion.

All Risankizumab Treated (ALL RZB) Population:

The All Risankizumab Treated Population consists of subjects who received at least one dose of risankizumab in this Study M15-997. This population will be used to provide a comprehensive summary of safety, and will be summarized by risankizumab 150 mg, and by any dose of risankizumab.

5.2 Variables Used for Stratification of Randomization

For this open-label study, no randomization of subjects into different treatment groups or stratification of randomization is required.

6.0 Analysis Conventions

Since this is an open-label continuation study, no statistical test will be conducted. Summary statistics will be provided. Data from preceding studies will be integrated with data from this study in the summaries.

Definition of Baseline

For this study, the following two types of baseline values are defined.

1. Preceding Study Baseline Value (BL): These values represent the baseline values of preceding studies, that is, the last non-missing values on or before the date of the first dose of study drug in the preceding study. For vital sign assessments, only assessments prior to first dose time will be considered, since vital signs are to be assessed both pre- and post-dose in some visits. The efficacy analysis based on RZB, RZB_NL, Retreatment, UST_RZB, ADA_RZB, FUM_RZB, and RZB_Japan populations will use these baseline values. These baseline values will be referred to as "BL" in this document. Unless otherwise specified, this will be the "baseline" for analysis.
2. RZB baseline value (BL_RZB): These values are the last non-missing values on or before the date of the first dose of risankizumab in the preceding study or Study M15-997. For vital sign assessments, only assessments prior to first dose time will be considered, since vital signs are to be assessed both pre- and post-dose in some visits. These values will be referred to as BL_RZB in this document. BL_RZB will be used for safety analyses in all populations.

Definition of Final Observation (Applicable to Safety Analyses)

Final observation in the entire study is defined as the last non-missing observation collected within 140 days after the last dose of risankizumab.

Definition of Rx Days (Days Relative to the Date of First Dose of Study Drug)

Rx days are calculated for each time point relative to the date of first dose of risankizumab in the corresponding study period. They are defined as the number of days between the day of the first dose of risankizumab and the specific time point. Rx days are negative values when the time point of interest is prior to the first risankizumab dose day. Rx days are positive values when the time point of interest is on or after the first risankizumab dose day. The day of the first dose of risankizumab is defined as Rx Day 1, while the day prior to the first risankizumab dose is defined as Rx Day -1 (there is no Rx Day 0).

Definition of Analysis Windows

All time points and corresponding time windows are defined based on Rx Days.

For efficacy analyses, local tolerability, laboratory parameters, and vital sign variables, analysis windows are constructed using the following algorithm:

- Determine the nominal Rx day for each visit (e.g., Week 4 [4 weeks after Baseline visit] equals Rx Day 29).
- In order to include all post baseline data, the first post-baseline interval starts on the first day after the first dose of risankizumab (Rx Day 2).
- Determine the window around a specific nominal Rx day by adding or subtracting half of the interval between adjacent visits (e.g., days between Week 2 and Week 4 is 14). The threshold between adjacent visits is determined by splitting the interval evenly between the visits. If the resulting split is between Rx days, then the threshold is determined as the midpoint between the adjacent visits. If the resulting split is on an Rx day, then the threshold is determined as being between that Rx day and the Rx day prior to it (e.g., the split between Week 2 and Week 4 would be between Rx Days 22 and 23).
- If more than one assessment is included in a time window the assessment closest to the nominal day will be used. If there are two observations

equidistant to the nominal day, the one after the nominal day will be used in analyses. If more than one post baseline assessment is included on the same day, then the worst assessment on that day will be used in analyses, except those specified in Section 11.0.

The protocol specified visits and corresponding time windows used in the efficacy analyses, local tolerability, laboratory parameters, and vital sign variables, are presented in the following tables.

Table 1. Visit Windows for Analysis of PASI, sPGA, Local Tolerability Assessment, Clinical Laboratory Tests, and Vital Signs (RZB Population)

Window Label	Target Day	Interval
Baseline ^a	1	≤ 1 ^b
Week 4	29	[2, 43]
Week 8	57	[44, 71]
Week 12	85	[72, 99]
Week 16	113	[100, 155]
Week 28	197	[156, 239]
Week 40	281	[240, 323]
Week 52	365	[324, 407]
Week 64	449	[408, 491]
Week 76	533	[492, 575]
Week 88	617	[576, 659]
Week 100	701	[660, 743]
Week 112	785	[744, 827]
Week 124	869	[828, 911]
Week 136	953	[912, 995]
Week 148	1037	[996, 1079]
Week 160	1121	[1080, 1163]
Week 172	1205	[1164, 1247]
Week 184	1289	[1248, 1331]
Week 196	1373	[1332, 1415]
Week 208	1457	[1416, 1541]
Week 232	1625	[1542, 1709]
Week 256	1793	[1710, 1877]
Week 280	1961	[1878, 2045]
Week 304	2129	[2046, 2199]

a. There is no baseline for local tolerability measurements.

b. If time is collected in vital signs, restrict to records prior to the first dose of study drug.

Note: Rx Day calculated relative to first dose date of risankizumab.

Table 2. Visit Windows for Analysis of Efficacy Variables (DLQI/NAPSI/PSSI/PPASI) (RZB Population)

Window Label	Target Day	Interval
Baseline	1	≤ 1
Week 16	113	[2, 239]
Week 52	365	[240, 449]
Week 76	533	[450, 617]
Week 100	701	[618, 785]
Week 124	869	[786, 953]
Week 148	1037	[954, 1121]
Week 172	1205	[1122, 1289]
Week 196	1373	[1290, 1415]
Week 208	1457	[1416, 1541]
Week 232	1625	[1542, 1709]
Week 256	1793	[1710, 1877]
Week 280	1961	[1878, 2045]
Week 304	2129	[2046, 2199]

Note: Rx Day calculated relative to first dose date of risankizumab.

Table 3. Visit Windows for Analysis of PASI, sPGA, Local Tolerability Assessment, Clinical Laboratory Tests, and Vital Signs (RZB_NL Population)

Window Label	Target Day	Interval
Switch to RZB	1	$\leq 1^a$
Week 12S	85	[2, 127]
Week 24S	169	[128, 211]
Week 36S	253	[212, 295]
Week 48S	337	[296, 379]
Week 60S	421	[380, 463]
Week 72S	505	[464, 547]
Week 84S	589	[548, 631]
Week 96S	673	[632, 715]
Week 108S	757	[716, 799]
Week 120S	841	[800, 883]
Week 132S	925	[884, 967]
Week 144S	1009	[968, 1051]
Week 156S	1093	[1052, 1135]
Week 168S	1177	[1136, 1219]
Week 180S	1261	[1220, 1303]
Week 192S	1345	[1304, 1429]
Week 216S	1513	[1430, 1597]
Week 240S	1681	[1598, 1765]
Week 264S	1849	[1766, 1933]
Week 288S	2017	[1934, 2087]

S = Switch to Risankizumab

a. If time is collected in vital signs, restrict to records prior to the first dose after switch to RZB.

Note: Rx Day calculated relative to first dose date of risankizumab for subjects switched from Placebo.

**Table 4. Visit Windows for Analysis of Efficacy Variables
 (DLQI/NAPSI/PSSI/PPASI) (RZB_NL Population)**

Window Label	Target Day	Interval
Switch to Risankizumab	1	≤ 1
Week 36S	253	[2, 337]
Week 60S	421	[338, 505]
Week 84S	589	[506, 673]
Week 108S	757	[674, 841]
Week 132S	925	[842, 1009]
Week 156S	1093	[1010, 1177]
Week 180S	1261	[1178, 1303]
Week 192S	1345	[1304, 1429]
Week 216S	1513	[1430, 1597]
Week 240S	1681	[1598, 1765]
Week 264S	1849	[1766, 1933]
Week 288S	2017	[1934, 2087]

S = Switch to Risankizumab

Note: Rx Day calculated relative to first dose date of risankizumab for subjects switched from Placebo.

Table 5. Visit Windows for PASI and sPGA (Relapsed and Retreatment Subjects in Retreatment Population)

Window Label	Target Day	Interval
Entry of Retreatment	1	≤ 1
Week 8R	57	[2, 85]
Week 16R	113	[86, 155]
Week 28R	197	[156, 239]
Week 40R	281	[240, 323]
Week 52R	365	[324, 407]
Week 64R	449	[408, 491]
Week 76R	533	[492, 575]
Week 88R	617	[576, 659]
Week 100R	701	[660, 743]
Week 112R	785	[744, 827]
Week 124R	869	[828, 911]
Week 136R	953	[912, 995]
Week 148R	1037	[996, 1079]
Week 160R	1121	[1080, 1163]
Week 172R	1205	[1164, 1289]
Week 196R	1373	[1290, 1457]
Week 220R	1541	[1458, 1625]
Week 244R	1709	[1626, 1793]
Week 268R	1877	[1794, 1961]
Week 292R	2045	[1962, 2115]

R = Retreatment of Risankizumab

Note: Rx Day calculated relative to first dose date of retreatment with risankizumab.

Table 6. Visit Windows for PASI and sPGA (OLE Retreated Subjects in Retreatment Population)

Window Label	Target Day	Interval
Entry of OLE	1	≤ 1
Week 12R	85	[2, 127]
Week 24R	169	[128, 211]
Week 36R	253	[212, 295]
Week 48R	337	[296, 379]
Week 60R	421	[380, 463]
Week 72R	505	[464, 547]
Week 84R	589	[548, 631]
Week 96R	673	[632, 715]
Week 108R	757	[716, 799]
Week 120R	841	[800, 883]
Week 132R	925	[884, 967]
Week 144R	1009	[968, 1051]
Week 156R	1093	[1052, 1177]
Week 180R	1261	[1178, 1345]
Week 204R	1429	[1346, 1513]
Week 228R	1597	[1514, 1681]
Week 252R	1765	[1682, 1849]

R = Retreatment of Risankizumab

Note: Rx Day calculated relative to first dose date of retreatment with risankizumab.

Table 7. Visit Windows for DLQI, NAPSI, PSSI, and PPASI (OLE Retreated Subjects in Retreatment Population)

Window Label	Target Day	Interval
Entry of OLE	1	≤ 1
Week 24R	169	[2, 253]
Week 48R	337	[254, 421]
Week 72R	505	[422, 589]
Week 96R	673	[590, 757]
Week 120R	841	[758, 925]
Week 144R	1009	[926, 1093]
Week 156R	1093	[1094, 1177]
Week 180R	1261	[1178, 1345]
Week 204R	1429	[1346, 1513]
Week 228R	1597	[1514, 1681]
Week 252R	1765	[1682, 1849]

R = Retreatment of Risankizumab

Note: Rx Day calculated relative to first dose date of retreatment with risankizumab.

Table 8. Visit Windows for PASI, sPGA, Local Tolerability Assessment, Clinical Laboratory Tests, and Vital Signs (ADA_RZB Population)

Window Label	Target Day	Interval
Switch at Week 16		RxDay_B
Switch to Risankizumab	1	$\leq 1^a$
Week 4S	29	[2, 43]
Week 8S	57	[44, 71]
Week 12S	85	[72, 99]
Week 16S	113	[100, 127]
Week 20S	141	[128, 155]
Week 24S	169	[156, 183]
Week 28S	197	[184, 239]
Week 40S	281	[240, 323]
Week 52S	365	[324, 407]
Week 64S	449	[408, 491]
Week 76S	533	[492, 575]
Week 88S	617	[576, 659]
Week 100S	701	[660, 743]
Week 112S	785	[744, 827]
Week 124S	869	[828, 911]
Week 136S	953	[912, 995]
Week 148S	1037	[996, 1079]
Week 160S	1121	[1080, 1163]
Week 172S	1205	[1164, 1247]
Week 184S	1289	[1248, 1373]
Week 208S	1457	[1374, 1541]
Week 232S	1625	[1542, 1709]
Week 256S	1793	[1710, 1877]
Week 280S	1961	[1878, 2031]

Table 8. Visit Windows for PASI, sPGA, Local Tolerability Assessment, Clinical Laboratory Tests, and Vital Signs (ADA_RZB Population) (Continued)

Window Label	Target Day	Interval
Switch at OLE		RxDay_OL
Entry of OLE	1	$\leq 1^a$
Week 12S	85	[2, 127]
Week 24S	169	[128, 211]
Week 36S	253	[212, 295]
Week 48S	337	[296, 379]
Week 60S	421	[380, 463]
Week 72S	505	[464, 547]
Week 84S	589	[548, 631]
Week 96S	673	[632, 715]
Week 108S	757	[716, 799]
Week 120S	841	[800, 883]
Week 132S	925	[884, 967]
Week 144S	1009	[968, 1051]
Week 156S	1093	[1052, 1177]
Week 180S	1261	[1178, 1345]
Week 204S	1429	[1346, 1513]
Week 228S	1597	[1514, 1681]
Week 252S	1765	[1682, 1835]

S = Switch to Risankizumab

a. If time is collected in vital signs, restrict to records prior to the first dose after switch to RZB.

Note: RxDay_B calculated relative to the first dose date in Part B.

RxDay_OL calculated relative to the first dose date of OLE.

Table 9. Visit Windows for NAPSI, PPASI, PSSI, and DLQI (ADA_RZB Population)

Window Label	Target Day	Interval
Switch at Week 16		RxDay_B
Switch to Risankizumab	1	≤ 1
Week 28S	197	[2, 281]
Week 52S	365	[282, 449]
Week 76S	533	[450, 617]
Week 100S	701	[618, 785]
Week 124S	869	[786, 953]
Week 148S	1037	[954, 1121]
Week 172S	1205	[1122, 1247]
Week 184S	1289	[1248, 1373]
Week 208S	1457	[1374, 1541]
Week 232S	1625	[1542, 1709]
Week 256S	1793	[1710, 1877]
Week 280S	1961	[1878, 2031]
Switch at OLE		RxDay_OL
Entry of OLE	1	≤ 1
Week 24S	169	[2, 253]
Week 48S	337	[254, 421]
Week 72S	505	[422, 589]
Week 96S	673	[590, 757]
Week 120S	841	[758, 925]
Week 144S	1009	[926, 1051]
Week 156S	1093	[1052, 1177]
Week 180S	1261	[1178, 1345]
Week 204S	1429	[1346, 1513]
Week 228S	1597	[1514, 1681]
Week 252S	1765	[1682, 1835]

S = Switch to Risankizumab

Note: RxDay_B calculated relative to the first dose date in Part B.

RxDay_OL calculated relative to the first dose date of OLE.

Table 10. Visit Windows for Analysis of PASI, sPGA, Local Tolerability Assessment, Clinical Laboratory Tests, and Vital Signs (UST_RZB, FUM_RZB, RZB_Japan Populations)

Window Label	Target Day	Interval
Entry of Study M15-997	1	≤ 1 ^a
Week 12	85	[2, 127]
Week 24	169	[128, 211]
Week 36	253	[212, 295]
Week 48	337	[296, 379]
Week 60	421	[380, 463]
Week 72	505	[464, 547]
Week 84	589	[548, 631]
Week 96	673	[632, 715]
Week 108	757	[716, 799]
Week 120	841	[800, 883]
Week 132	925	[884, 967]
Week 144	1009	[968, 1051]
Week 156	1093	[1052, 1177]
Week 180	1261	[1178, 1345]
Week 204	1429	[1346, 1513]
Week 228	1597	[1514, 1681]
Week 252	1765	[1682, 1835]

a. If time is collected in vital signs, restrict to records prior to the first dose of RZB in Study M15-997.

Note: Rx Day calculated relative to first dose date of risankizumab.

Table 11. Visit Windows for Analysis of NAPSI, PPASI, PSSI, and DLQI (UST_RZB, FUM_RZB, RZB_Japan Populations)

Window Label	Target Day	Interval
Entry of Study M15-997	1	≤ 1
Week 24	169	[2, 253]
Week 48	337	[254, 421]
Week 72	505	[422, 589]
Week 96	673	[590, 715]
Week 108	757	[716, 799]
Week 120	841	[800, 925]
Week 144	1009	[926, 1051]
Week 156	1093	[1052, 1177]
Week 180	1261	[1178, 1345]
Week 204	1429	[1346, 1513]
Week 228	1597	[1514, 1681]
Week 252	1765	[1682, 1835]

Note: Rx Day calculated relative to first dose date of risankizumab.

Definition of Missing Data Imputation

No global imputation is taking place at the database level. Efficacy related imputations are outlined in Section 10.0. There is no imputation for missing values in the safety analyses.

Rounding of Numeric Results

Rounding will be performed for presentation of results. No rounding will be performed before or during analyses. The ROUND function of SAS will be used to round results.

When dichotomizing continuous variables, associated continuous variables will be rounded to 9 decimal points before applying the cutoff point to determine the response status (for example, percent change from baseline in PASI score will be rounded to 9 decimal places before comparing to 90%).

The mean and median will be rounded for presentation to 1 decimal more than the data entered into the database. The standard deviation will be rounded to 2 decimal places more than the data entered into the database. The minimum and maximum values will be presented as entered into the database.

Probabilities will be rounded to 3 decimal places before assignment of statistical significance and will be presented in rounded format. Probabilities that round to zero or are reported by SAS as zero will be presented as "< 0.001." Probabilities that round to 1 or are reported by SAS as 1 will be presented as "> 0.999."

7.0 Demographics, Baseline Characteristics, Medical History, and Previous/Concomitant Medications

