4.2 Design Diagram

This is a Phase 3, single-arm, multicenter, OLE study designed to investigate the long term safety and efficacy of risankizumab 150 mg E12W in the treatment of moderate to severe chronic plaque psoriasis. Approximately 2200 subjects who meet the entry criteria are planned to be enrolled in this study, rolling over from the preceding Studies 1311.3, 1311.4, 1311.13, 1311.28, 1311.30, 1311.38, and M16-178 (Phase 2/3, randomized clinical studies in subjects with moderate to severe chronic plaque psoriasis, conducted by Boehringer Ingelheim or AbbVie).

All subjects need to complete one of the preceding Phase 2/3 psoriasis studies. The subject preferably has the Baseline visit of Study M15-997 on the same day of the completion visit of the preceding study; however, the Baseline visit can be delayed up to 8 weeks if needed. All subjects will be administered 150 mg risankizumab s.c. at the Baseline visit, and from the Baseline visit onwards, risankizumab will be administered subcutaneously E12W during the study. Study visits for dosing, efficacy and safety assessments will be performed E12W starting from Baseline until the Week 156 visit. After this visit until the End of Treatment (EOT) visit at Week 252, study visits will be performed E24W. The schematic of the study is shown in [Figure 1](#).

Figure 1. Study Schematic

There is a ± 7 days visit window for study visits. Every effort will be made to bring subjects back to their original scheduled visit (calculated from Baseline) if they are out of the visit window. Subjects who discontinue study drug treatment early will need to attend an early EOT visit ideally within 2 weeks after the decision and preferably prior to the administration of any new therapies.

All subjects, including those that prematurely discontinued study drug treatment, will return to the clinic for an End of Observation Visit (EOO) 20 weeks after their last administered dose of risankizumab. Study completion is defined as a subject having completed the EOO visit.

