4.4 Interim Analysis

The first interim analysis was performed in 2017, after the last patient in Study 1311.4 either had completed Week 52 visit or discontinued from the study, and at the time approximate to the database lock of all other preceding studies, whichever occurs later, to generate sufficient evidence for long-term safety and efficacy of risankizumab in subjects with psoriasis.

To support regulatory activities in Switzerland, a second interim analysis will be conducted to include all available patient data up to the data cut-off date of November 01, 2021.

Additional interim analyses may be performed based on regulatory or other requirements.

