10.0 Efficacy Analysis

10.1 General Considerations

The efficacy analysis will be performed for each population except the ALL_RZB Population. The efficacy analysis will use the data from this study and preceding study after subjects started to take risankizumab. The BL values (baseline values from the

preceding studies) will be used to determine responses and changes in the efficacy variables.

Continuous variables will be summarized by the number of observations, mean, standard deviation, median, minimum, maximum, 25th and 75th percentiles, as well as the 95% confidence intervals (CIs) of the mean values. Categorical variables will be summarized by counts and percentages, as well as the 95% CIs of the percentages. No statistical tests will be performed in this study.

Missing data will be imputed using the following methods for the efficacy analyses:

- Last Observation Carried Forward (LOCF): The LOCF analyses will use the last observed non-missing evaluation (last completed non-missing evaluation, from composite endpoint) from the previous visit within the particular period for efficacy measures assessed to impute missing data at later visits in the same period. Baseline efficacy evaluations will not be carried forward. Of note, post-baseline observations from Part A1 in Study 1311.4 can be carried forward to ITT_A2 subjects from ARM 1 since treatment is the same.
- As-Observed Cases (OC): The as-observed analysis will not impute values for missing evaluations, and thus a subject who does not have an evaluation on a scheduled visit will be excluded from the as-observed analysis for that visit.

LOCF will be used as the primary imputation method and OC will be used as sensitivity analysis for both categorical variables and continuous variables. Both LOCF and OC will not include values after discontinuation of study drug.

All endpoints will be analyzed up to the last visit with at least one subject has observed measurements of that variable, by the time of the interim data cutoff.

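### The RZB_NL windows (SAP Tables 3 and 4) close at Day 2087; if Study 1311.4 placebo-switch subjects had more than 46 weeks between switch and OLE entry, their end-of-treatment visits have no window

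*SAP*

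**What the plan says.** SAP 5.1 defines RZB_NL as subjects "randomized to placebo in the initial study and switched to risankizumab 150 mg (without loading dose) in Studies 1311.3, 1311.4, 1311.28, and 1311.38". SAP 6.0 gives this population one set of windows: Table 3, titled "Visit Windows for Analysis of PASI, sPGA, Local Tolerability Assessment, Clinical Laboratory Tests, and Vital Signs (RZB_NL Population", and Table 4 for DLQI, NAPSI, PSSI and PPASI. The clock is set by the table note: "Rx Day calculated relative to first dose date of risankizumab for subjects switched from Placebo". Both tables change to 24-week spacing at Week 192S and end at Week 288S, with target Day 2017 and interval [1934, 2087]. There is no row for a later assessment and no rule on how to handle one.

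SAP 4.2 puts end of treatment at OLE Week 252: "After this visit until the End of Treatment (EOT) visit at Week 252, study visits will be performed E24W". On entry to the OLE it says "however, the Baseline visit can be delayed up to 8 weeks if needed".

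Neither document gives the length of 1311.4 or the week its placebo subjects switched. SAP 4.4 timed the first interim analysis "after the last patient in Study 1311.4 either had completed Week 52 visit or discontinued from the study", and set this against the database lock of all the other preceding studies. SAP 5.1 and 10.1 show that 1311.4 had Parts A1, A2 and B, with re-randomization to placebo in Part B and later retreatment. Table 5, for subjects who relapsed and were retreated, runs to Week 292R and closes at Day 2115.

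**The concern.** The grid follows the calendar of a 52-week feeder but also serves a study with a different and apparently longer design. If 1311.4 placebo-switch subjects entered the OLE much later than 36 weeks after their switch, their last OLE visits come after Day 2087 and enter no by-visit summary.

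Such subjects would have the longest continuous risankizumab exposure in RZB_NL. Their late PASI, sPGA, DLQI, laboratory, vital-sign and local-tolerability results are part of the long-term evidence the study is run to collect. LOCF, the primary imputation method, could also fill an empty Week 288S cell with an older value although a later observation exists. SAP 6.0 opens the first interval at Day 2 so that all post-baseline data are included. It takes no matching care at the other end.

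**Working it through.** **Reproducing the plan's grid.** Target day = 7 × week + 1, and window edges are midpoints between adjacent targets (SAP 6.0). All Table 3 intervals reproduce up to the last upper edge.
- Change of spacing: 192 = 36 + 156. Last row: 288 = 36 + 252, and 7 × 288 + 1 = 2017. Both put OLE entry at Week 36S.
- 36 + 16 = 52, so the grid fits a 52-week feeder with a switch at Week 16. The Week 16 switch is an assumption. Protocol 3.0 places the placebo comparison at Week 16 in the four pivotal studies.
- The last window closes 2087 − 2017 = 70 days after its target. For a 52-week feeder that covers an 8-week gap (56 days) and the 7-day visit window: 56 + 7 = 63.

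**When OLE visits leave the grid.** Let F be the weeks from switch to feeder completion plus the roll-over gap. OLE Week w falls on Day 7 × (F + w) + 1. The last window closes at (2087 − 1) / 7 = 298 weeks.
- Week 252 is outside when F > 298 − 252 = 46.
- Week 228 is outside when F > 298 − 228 = 70.
- Week 204 is outside when F > 298 − 204 = 94.

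With a Week 16 switch and no gap, the feeder-length thresholds are 62, 86 and 110 weeks. With an 8-week gap they are 54, 78 and 102. The lengths below are assumed.

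| Feeder length (weeks) | Day of OLE Week 252, no gap | Day of OLE Week 252, 8-week gap | On-time OLE visits after Day 2087 |
|---|---|---|---|
| 52 | 2017 | 2073 | none |
| 56 | 2045 | 2101 | 252 with the gap only |
| 62 | 2087 | 2143 | 252 with the gap only |
| 64 | 2101 | 2157 | 252 |
| 68 | 2129 | 2185 | 252 |
| 88 | 2269 | 2325 | 228, 252 |
| 104 | 2381 | 2437 | 228, 252; also 204 with the gap |

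**What the documents imply about 1311.4.** SAP 10.1 allows carry-forward from Part A1 to A2 for ARM 1 because its treatment is unchanged. This suggests that another arm changed treatment at A2, so that placebo subjects switched before Part B. If so, and if both groups completed at the same study week, F for a placebo-switch subject equals s plus pre-OLE retreatment time plus gap. Here s is the time from the placebo switch to the first retreatment dose. Table 5 bears on retreatment time plus gap:
- Last row: 292 = 40 + 252, so the table accommodates 40 weeks. Then F > 46 needs s > 46 − 40 = 6.
- Row 268R closes at Day 1961, which is 280 weeks. Row 292R is therefore needed for an on-time Week 252 only if retreatment plus gap exceeds 280 − 252 = 28 weeks. Then s of 46 − 28 = 18 weeks or more is enough.
- Change of spacing: 172 = 16 + 156, which points to entry at 16R. If 292R is a spare row, s must exceed 46 − 16 = 30.

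If re-randomization came no earlier than the Week 28 dose (inferred from the dosing grid in Protocol 5.6.4) and retreatment lasted 40 weeks, the feeder ran at least 28 + 40 = 68 weeks. Week 252 is then at or after Day 2129, 42 days outside. If re-randomization was at Week 16, the bound is only 16 + 40 = 56 weeks, and Day 2045 is inside when there is no gap.

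**LOCF at Week 288S.** The window holds an on-time visit when 276 < F + w ≤ 298, a span of 22 weeks against 24-week visits. With on-time visits it is empty only for 46 < F ≤ 48 or 70 < F ≤ 72 (feeders of 64 and 88 weeks sit on the upper edges). Outside those bands it is empty if the visit that belongs there was missed. In each case LOCF would use an earlier value although a later observation exists.

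**The case against.** The strongest objection is that no loss is shown. The length, switch week and re-randomization week of 1311.4 are not in the documents, and running past Week 52 is not enough, because the 70-day margin absorbs feeders up to 62 weeks with prompt roll-over. SAP 4.4 gives no length. Table 5 gives mixed signals: its last row points to entry at 40R and its change of spacing to 16R, so it may cover a range of entry times or contain a spare row. All of this stands, and it is why the point is conditional.

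A reader might also infer that the SAP contradicts itself, since SAP 10.1 says "All endpoints will be analyzed up to the last visit with at least one subject has observed measurements of that variable". That sentence goes on to tie itself to the interim data cutoff, and SAP 10.4 repeats it for the interim analysis. It sets how far tables run at an interim and does not promise every final assessment a window.

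A reader might infer that safety evidence is lost. Treatment-emergent adverse events, event rates, worst-value shifts and potentially clinically important values do not depend on the last visit window. The safety final observation is the last value within 140 days of the last dose. For subjects from Japan, data after the start of the 75 mg dose are excluded from RZB_NL in any case.

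Ending a shared grid where most feeders end is also defensible, and added rows would be harmful if LOCF ran into them for subjects never scheduled there. That argues for restricting the rows. It does not answer what happens to assessments after Day 2087.

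**Conclusion.** The concern holds as a conditional one. The RZB_NL grid can absorb at most 46 weeks between switch and OLE entry. 1311.4 belongs to the population, and its withdrawal-and-retreatment design, the SAP 4.4 timing and Table 5 make a longer interval plausible. Above 46 weeks one by-visit assessment per 1311.4 placebo-switch subject has no window, and above 70 weeks two. Above 94 weeks, reached at an assumed 104-week feeder with an 8-week gap, it is three.

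The documents do not support stating the loss as fact, and the number of subjects affected is unknown. The feeder-length thresholds rest on a Week 16 switch; the 46- and 70-week limits do not. The effect is confined to by-visit summaries and LOCF values at Week 288S in a descriptive study. The change is worth making because it is cheap and protects the latest observations in the population.

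**What to change.** State in SAP 6.0 the 1311.4 schedule: total length, placebo-switch week and longest possible time from switch to OLE entry. If that time, including the 8-week gap, cannot exceed 46 weeks, say so; for a visit within its 7-day window also to be covered, it must not exceed 45 weeks.

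Otherwise extend Tables 3 and 4 to the latest possible OLE Week 252, Day 7 × (F + 252) + 1 for the largest F, plus 7 days. Continuing the present rule gives Week 312S (Day 2185) and Week 336S (Day 2353), with the Week 288S upper bound reset to (2017 + 2185) / 2 = 2101.

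Check these targets against the real visit days first. At an assumed 88 weeks with no gap, OLE Week 228 falls on Day 2101 and Week 252 on Day 2269 = (2185 + 2353) / 2. Both are window midpoints, so the permitted 7 days either way would split each visit across two rows. A 1311.4-specific grid with targets on its actual OLE visit days avoids this.

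Restrict the added rows, including LOCF and denominators, to 1311.4 subjects and footnote this. Check the last row of Table 5 in the same way: Day 2115 is (2115 − 1) / 7 = 302 weeks, so it covers up to 302 − 252 = 50 weeks of retreatment plus gap before the OLE.

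The cost is a few table rows, a little programming and small numbers in the added rows.
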